2. ABBREVIATIONS

Abbreviations pertain to the Statistical Analysis Plan (SAP) only (not the tables, figures and listings [TFLs]).

AE	Adverse event
AUC	Area under the concentration versus time curve
C _{max}	Maximum observed drug concentration
CI	Confidence interval
CRF	Case Report Form
CSR	Clinical Study Report
CRU	Clinical Research Unit
CV	Coefficient of variation
EC	Early Clinical
ECG	Electrocardiogram
e.g.	For example (Latin: exempli gratia)
ICH	International Council on Harmonisation
MedDRA	Medical Dictionary for Regulatory Activities
PD	Pharmacodynamic
PK	Pharmacokinetic
SAP	Statistical Analysis Plan
SC	Subcutaneous
SD	Standard deviation
TFLs	Tables, Figures, and Listings
t _{1/2}	Half-life associated with the terminal rate constant (λ_z) in non-compartmental analysis
t _{max}	Time of maximum observed drug concentration

3. INTRODUCTION

This SAP has been developed after review of the Clinical Study Protocol (final version dated 17 August 2016).

This SAP describes the planned analysis of the safety, tolerability, pharmacokinetic (PK) and pharmacodynamic (PD) data from this study. A detailed description of the planned TFLs to be presented in the clinical study report (CSR) is provided in the accompanying TFL shell document.

The intent of this document is to provide guidance for the statistical, PD and PK analyses of data. In general, the analyses are based on information from the protocol, unless they have been modified by agreement between Eli Lilly and Company and Covance Early Clinical (EC) Biometrics. A limited amount of information concerning this study (e.g., objectives, study design) is given to help the reader's interpretation. This SAP must be signed off prior to first subject administration for this study. When the SAP and TFL shells are agreed upon and finalized, they will serve as the template for this study's CSR.

This SAP supersedes the statistical considerations identified in the protocol; where considerations are substantially different, they will be so identified. If additional analyses are required to supplement the planned analyses described in this SAP, they may be performed and will be identified in the CSR. Any substantial deviations from this SAP will be agreed upon between Eli Lilly and Company and Covance EC Biometrics and identified in the CSR. Any minor deviations from the TFLs may not be documented in the CSR.

This SAP is written with consideration of the recommendations outlined in the International Council on Harmonisation (ICH) E9 Guideline entitled Guidance for Industry: Statistical Principles for Clinical Trials¹ and the ICH E3 Guideline entitled Guidance for Industry: Structure and Content of Clinical Study Reports².

4. STUDY OBJECTIVES

Primary Objective

The primary objective of this study is to evaluate the PK and PD profiles of LY3185643 and rGlucagon after single doses of study treatment.

Secondary Objective

To evaluate the safety and tolerability of LY3185643 after single doses of study treatment.

Exploratory Objective

To evaluate immunogenicity of LY3185643 after multiple single doses of study treatment.

5. STUDY DESIGN

This study is a Phase 1, single-center, subject- and investigator-blind, randomized, 9-way, 3-period crossover study in healthy subjects to evaluate the PK and PD of LY3185643 and rGlucagon after subcutaneous (SC) administration.

Up to 27 healthy men and women may be enrolled to target approximately 18 subjects to complete the study. Each subject will receive 3 doses on each of 3 dosing days (total of 9 doses: 5 doses of LY3185643 and 4 doses of rGlucagon) administered SC. Doses will be administered in a 9-way complete crossover design in 3 periods, and subjects will be randomized to predefined treatment sequences. Completers are defined as subjects who have received all 9 doses.

Subjects will be required to attend the Clinical Research Unit (CRU) on at least 5 occasions:

- 1 screening visit (may occur up to 28 days before randomization)
- 3 treatment periods
- 1 follow-up visit (at least 30 days after completing the last dose of study treatment)

Each treatment period will consist of 3 days (Days -1 to 2). Subjects should return for the next period with a minimum of 3 days between treatment periods. On Day -1, subjects will be admitted to the CRU. Subjects will be provided a carbohydrate-rich meal in the evening at approximately 10:00 PM and will remain fasted until completion of the study procedures on Day 1. On Day 1, study drug will be administered SC as follows:

- Dose 1: morning of Day 1
- Dose 2: approximately 4 hours after administration of the first dose
- Dose 3: approximately 4 hours after administration of the second dose

Blood samples will be collected for the determination of concentrations of LY3185643, glucagon, glucose, C-peptide, and for immunogenicity as shown in the Schedule of Activities. Blood samples for measurement of glucose concentrations using YSI glucose analyzer will also be collected.

Safety data will include clinical examinations, vital signs, elec trocardiograms (ECGs; including telemetry, holter monitoring), clinical laboratory tests, concomitant medications and a record of adverse events (AEs).

All study procedures will end approximately 4 hours after the third dose. Subjects will be provided dinner and stay overnight in the CRU for observation. Subjects will be discharged the following day (Day 2) after completion of all assessments as shown in the Schedule of Activities.

Figure 1 illustrates the study design:

Period 1				Periods 2 and 3			Summary			
	Day -1	Day 1			Day 2					
Cohort A	Admit to CRU	Dose	Dose	Dose	Stay Overnight D/C home	The scheme on the left is repeated for Period 2 and Period 3.				
Cohort B		Dose	Dose	Dose						
Cohort C		Dose	Dose	Dose						
Period 2				Period 3						
Day -1				Day 1			Day 2			
Cohort D	Admit to CRU	Dose	Dose	Dose	Stay Overnight D/C home					
Cohort E		Dose	Dose	Dose						
Cohort F		Dose	Dose	Dose						
Period 2				Period 3						
Day -1				Day 1			Day 2			
Cohort G	Admit to CRU	Dose	Dose	Dose	Stay Overnight D/C home					
Cohort H		Dose	Dose	Dose						
Cohort I		Dose	Dose	Dose						

Abbreviations: CRU = clinical research unit; D/C = discharge.

Figure 1.

Approximately 18 subjects are expected to complete the study. Each subject will be randomized to 1 of 9 treatment sequences comprising single SC doses of LY3185643 or rGlucagon (Table 1). Subjects who discontinue may be replaced to target at least 18 completers; the replacement subject will be assigned the treatment sequence of the discontinued subject and complete all 3 treatment periods (total of 9 doses).

Cohort ^a	Treatment Period 1			Treatment Period 2			Treatment Period 3		
A	Dose 1	Dose 9	Dose 7	Dose 6	Dose 4	Dose 8	Dose 5	Dose 3	Dose 2
B	Dose 2	Dose 7	Dose 8	Dose 4	Dose 5	Dose 9	Dose 6	Dose 1	Dose 3
C	Dose 3	Dose 8	Dose 9	Dose 5	Dose 6	Dose 7	Dose 4	Dose 2	Dose 1
D	Dose 4	Dose 6	Dose 2	Dose 3	Dose 9	Dose 1	Dose 8	Dose 7	Dose 5
E	Dose 5	Dose 4	Dose 3	Dose 1	Dose 7	Dose 2	Dose 9	Dose 8	Dose 6
F	Dose 6	Dose 5	Dose 1	Dose 2	Dose 8	Dose 3	Dose 7	Dose 9	Dose 4
G	Dose 7	Dose 1	Dose 4	Dose 9	Dose 2	Dose 6	Dose 3	Dose 5	Dose 8
H	Dose 8	Dose 2	Dose 5	Dose 7	Dose 3	Dose 4	Dose 1	Dose 6	Dose 9
I	Dose 9	Dose 3	Dose 6	Dose 8	Dose 1	Dose 5	Dose 2	Dose 4	Dose 7

Note: This is an example table; subjects will be assigned a treatment sequence according to the actual treatment schedule provided to the site.

Dose assignment: Dose 1 = 10 µg LY3185643; Dose 2 = 25 µg LY3185643; Dose 3 = 50 µg LY3185643;
Dose 4 = 100 µg LY3185643; Dose 5 = 200 µg LY3185643; Dose 6 = 10 µg rGlucagon; Dose 7 = 25 µg
rGlucagon; Dose 8 = 50 µg rGlucagon; Dose 9 = 200 µg rGlucagon.

^a In each cohort, LY3185643 and rGlucagon will be administered.

Table 1.

6. TREATMENTS

The following is a list of the study treatment names that will be used in the TFLs.

Study Treatment Name	Treatment order in TFL
{Insert brief description of indication} 3185643	1
{Insert brief description of indication} 3185643	2
{Insert brief description of indication} 3185643	3
{Insert brief description of indication} 3185643	4
{Insert brief description of indication} 3185643	5
10 µg rGlucagon	6
25 µg rGlucagon	7
50 µg rGlucagon	8
200 µg rGlucagon	9

7. SAMPLE SIZE JUSTIFICATION

The sample size is customary for Phase 1 studies evaluating safety, PK, and/or PD parameters and is considered sufficient to evaluate the primary objective of this study.

Subjects who discontinue the study may be replaced so that at least 18 subjects complete the study. Replacement subjects will be assigned the treatment sequence of the subject that discontinued the study.

8. DEFINITION OF ANALYSIS POPULATIONS

The “Safety” population will consist of all subjects who received at least one dose of study drug, and have at least one postdose safety assessment.

The “Pharmacokinetic” population will consist of all subjects who received at least one dose of study drug and have evaluable PK data.

The “Pharmacodynamic” population will consist of all subjects who received at least one dose of study drug and have evaluable PD data.

All protocol deviations that occur during the study will be considered for their severity/impact and will be taken into consideration when subjects are assigned to analysis populations.

9. STATISTICAL METHODOLOGY

9.1 General

Data listings will be provided for all data that is databased. Summary statistics and statistical analysis will only be presented for data where detailed in this SAP. For continuous data, summary statistics will include the arithmetic mean, arithmetic standard deviation (SD), median, min, max and N; for log-normal data (e.g. the PK parameters: area under the concentration versus time curve [AUCs] and maximum observed drug concentration [C_{max}]) the geometric mean and geometric coefficient of variation (CV%) will also be presented. For categorical data, frequency count and percentages will be presented. Data listings will be provided for all subjects up to the point of withdrawal, with any subjects excluded from the relevant population highlighted. Summary statistics and statistical analyses will generally only be performed for subjects included in the relevant analysis population. For the calculation of summary statistics and statistical analysis, unrounded data will be used.

Mean change from baseline is the mean of all individual subjects' change from baseline values. Each individual change from baseline will be calculated by subtracting the individual subject's baseline value from the value at the timepoint t. The individual subject's change from baseline values will be used to calculate the mean change from baseline using a SAS procedure such as Proc Univariate.

Data analysis will be performed using SAS® Version 9.3 or greater.

9.2 Demographics and Subject Disposition

Subject disposition will be listed. The demographic variables age, sex, race, ethnicity, country of enrolment, site ID, body weight, height and body mass index will be summarized and listed.

9.3 Pharmacokinetic Assessment

9.3.1 Pharmacokinetic Analysis

PK parameter estimates for LY3185643 and rGlucagon will be calculated by standard noncompartmental methods of analysis.

The primary parameters for analysis will be C_{max} and AUC. Other noncompartmental parameters, such as $t_{1/2}$, apparent clearance, and apparent volume of distribution, may be reported. Population PK and exposure-response analyses may be performed using PK, PD and safety data.

PK parameters for LY3185643 and rGlucagon will be summarized for each dose group. Concentration-time profiles (mean and individual) will be generated. All PK data analyses will be the responsibility of the Lilly team.

9.3.2 Pharmacokinetic Statistical Methodology

PK parameter estimates (C_{max} and AUC) will be provided to Covance to delineate effects of dose proportionality for LY3185643 and rGlucagon separately using a power model as follows:

$$\log(PK_i) = \alpha + \beta \cdot \log(dose_i) + \varepsilon_i$$

Where i represents the i th subject, PK represents a PK parameter (AUC or C_{max}), and ε_i is a residual error term. The estimated ratios of dose-normalized means

$$\hat{R}_{dnm} = \left(\frac{h}{l} \right)^{\hat{\beta}-1}$$

and the corresponding 90% confidence intervals will be reported, where h and l denote the highest and lowest doses, respectively.

An example of the SAS code that will be used is as follows:

```
/* Lack of fit test */
proc mixed data=<indata>;
  class trtmnt vol;
  model l_pk = logdose trtmnt / htype=1 ddfm=kr;
  random intercept / subject=vol;
  ods output tests1=tests;
run;

/* Power model */
```

```
proc mixed data=<indata>;
  class vol;
  model l_pk = logdose / solution cl alpha=0.1 oupred=resids ddfm=kr;
  estimate ' x mg' intercept 1 logdose a / alpha=0.1 cl; /* a=Log value of x*/
  estimate ' y mg' intercept 1 logdose b / alpha=0.1 cl; /* b=Log value of y*/
  estimate ' z mg' intercept 1 logdose c / alpha=0.1 cl; /* c=Log value of z*/
  estimate 'z mg - x mg' logdose d / alpha=0.1 cl; /* d = Difference in log values of highest
  and lowest dose*/
  random intercept / subject=vol;
  ods output solutionf=estimate;
  ods output estimates=estims;
run;
```

Where l_pk is the log-transformed (base e) PK parameter.

Additional analyses may be conducted as appropriate.

9.4 Pharmacodynamic Assessment

9.4.1 Pharmacodynamic Analysis

The PD time-action and response of LY3185643 and rGlucagon will be compared to establish the relative potency between LY3185643 and rGlucagon.

The primary PD response variables of interest include t_{max} , C_{max} , change from baseline in C_{max} and change from baseline to each time point, and incremental AUCs for glucose measured by YSI glucose analyzer and C-peptide. Similar PD response variables using laboratory measured glucose will also be estimated.

9.4.2 Pharmacodynamic Statistical Methodology

All PD parameters including the baseline-corrected parameters will be summarized by dose group and tabulated. The individual observed and mean (by dose group) time profile of the PD measurements after dosing will be plotted.

For these parameters, a linear model will be fitted to account for the PD difference between LY3185643 and rGlucagon. The model is detailed below. In addition, partial AUC for glucose over appropriate time intervals will be calculated using the trapezoidal rule. The AUC for each subject after each dose will also be baseline-adjusted. Baseline for each dose will be defined as the average of predose values for that dose.

For each PD parameter, the linear model that is proposed to account for differences between LY3185643 and rGlucagon is:

$$Y_{kl} = \beta_0 + \beta_1 d_{kl} + \beta_2 d_{kl} * Z_{kl} + u_k + e_{kl} \quad (1)$$

where k denotes the subject index, l denotes the period index, d_{kl} is the dose in mg during each period, Z_{kl} is the treatment indicator (0 for rGlucagon and 1 for LY3185643), $u_k \sim NI(0, \sigma_{u^2})$ denotes the between subject error, and $e_{kl} \sim NI(0, \sigma_{e^2})$ denotes the within-subject error. The

notation “NI” means “Normally Independent.” There is no term for the treatment group indicator Z_{kl} because at dose = 0 the response should be the same for both treatment groups. Setting the mean responses for each treatment equal to each other, it follows that:

$$\beta_0 + \beta_1 D_1 + \beta_2 D_1 = \beta_0 + \beta_1 D_0$$

where D_0 denotes the rGlucagon dose and D_1 denotes the LY3185643 dose. It follows that $D_1 = \lambda D_0$ where $\lambda = \beta_1/(\beta_1 + \beta_2)$ is the conversion factor that determines how many mg of LY3185643 are equivalent to one mg of rGlucagon. The model (1) can be reparameterized as a nonlinear mixed model:

$$Y_{kl} = \beta_0 + \beta_1 d_{kl} + (1 - \lambda)/\lambda \beta_1 d_{kl} * Z_{kl} + u_k + e_{kl}.$$

Then, the conversion factor λ (the point estimate and the 90% confidence interval) will be directly estimated from this nonlinear model. This model may be extended to allow for multiple parameter values, if deemed appropriate.

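### SAP 9.4.2 estimates the conversion factor as a ratio of straight-line slopes in raw dose for every PD parameter, tmax included, with no planned check of linearity

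*SAP*

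**What the plan says.** For PD, SAP 9.4.2 states: "For each PD parameter, the linear model that is proposed to account for differences between LY3185643 and rGlucagon is" Y = β0 + β1·d + β2·d·Z + u + e. Here d is dose in mg, Z is 1 for LY3185643 and 0 for rGlucagon, u is a random subject effect and e is residual error. Treatment has no main effect "because at dose = 0 the response should be the same for both treatment groups". Equating the two mean responses gives λ = β1/(β1+β2), the mg of LY3185643 that match 1 mg of rGlucagon. The SAP then says "The model (1) can be reparameterized as a nonlinear mixed model" and plans a point estimate and 90% CI for λ. The only extension it names is to several parameters at once.

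The model applies to the parameters listed in SAP 9.4.1, which opens with tmax: "The primary PD response variables of interest include t_{max". None is exempted.

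For PK, SAP 9.3.2 fits a power model on the log scale and includes code for a "Lack of fit test". SAP 9.4.2 has no counterpart. It does promise that "All PD parameters including the baseline-corrected parameters will be summarized by dose group and tabulated".

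**The concern.** The reparameterized model is nonlinear in λ, not in dose, so it is still two straight lines. Their slope ratio is a relative potency over 10-200 µg only if both responses are linear in dose. Protocol 3.2.1 gives reason to wonder. Maximum glucose elevations came above 0.2 mg, and the protocol suggests feedback inhibition at high concentrations.

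Protocol 3.1 says that relative potency will help direct changes to the artificial pancreas control algorithms. Protocol 5.5 puts glucagon boluses in those systems at 5-50 µg. A conversion factor determined mainly by the 200 µg doses speaks to that range only through the unchecked assumption of linearity.

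The model suits tmax least. A time to peak response at dose zero has no clear meaning, so the stated reason for the common intercept does not carry over. If time to peak does not shift with dose, there is no slope from which to form a ratio.

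**Working it through.** The plan states no value of λ, no SD and no effect size, so there is no figure to reproduce. The checks below use the planned design.

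**Inputs from the documents.** Doses (Protocol Table APCA.5.1): LY3185643 10, 25, 50, 100 and 200 µg; rGlucagon 10, 25, 50 and 200 µg. At least 18 completers, each with all nine doses. With complete data and a random intercept, the fixed-effect fit equals least squares on the nine dose means.

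**Assumptions.** An Emax curve shared by both drugs, with LY3185643 dose divided by the true λ. The documents give no ED50, so a range is shown.

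**1. Algebra.** Take β1 = 3 and β2 = 1.2. Then λ = 3/4.2 = 0.714, and (1−λ)/λ × β1 = 1.2 = β2. The two forms are the same model. If the response is truly linear, λ is recovered exactly.

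**2. Where the information on λ comes from.** At λ = 1, β2 = 0, so ∂λ/∂β1 = β2/(β1+β2)² = 0 and Var(λ̂) ≈ Var(β̂2)/β1². The estimate β̂2 is a weighted sum of dose means, with weights from (X′X)⁻¹X′:

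| Dose (µg) | LY3185643 | rGlucagon |
|---|---|---|
| 10 | 0.051 | −0.369 |
| 25 | 0.349 | −0.702 |
| 50 | 0.845 | −1.256 |
| 100 | 1.838 | none |
| 200 | 3.824 | −4.580 |

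The squared weights sum to 35.60 at 200 µg, 3.38 at 100 µg and 3.04 at 50 µg or less, 42.02 in all. The shares are 84.7%, 8.0% and 7.2%. This step needs no curve assumption.

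**3. Noise-free fit of the straight-line model to the Emax curve.** Example: true λ 1, ED50 50 µg, Emax set to 1. The fitted slopes per mg are 2.857 for rGlucagon and 2.857 + 0.244 = 3.101 for LY3185643, so λ = 2.857/3.101 = 0.921.

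| ED50 (µg) | true 0.8 | true 1 | true 1.25 |
|---|---|---|---|
| 20 | 0.838 | 0.905 | 0.98 |
| 50 | 0.837 | 0.921 | 1.02 |
| 100 | 0.835 | 0.939 | 1.06 |
| 200 | 0.830 | 0.958 | 1.12 |
| 500 | 0.820 | 0.979 | 1.18 |

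The shortfall at true λ 1 arises because only LY3185643 has a 100 µg dose. Without that dose the fit gives 1.000 at every ED50. An ED50 of 20 µg fits Protocol 3.2.1 poorly, because 200 µg would already give 200/220 = 91% of Emax.

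**4. Coverage of the nominal 90% CI.** Simulation with assumed values: 18 subjects, mean response 60 mg/dL at 200 µg rGlucagon, between-subject SD 10, sensitivity CV 0 or 30%, residual SD 10 or 20 mg/dL, delta-method interval.

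- True 1: 75-88% at ED50 50-200, and 88-92% at ED50 500.
- True 1.25: 13-72% at ED50 50-200, and still below nominal at 500.
- True 0.8: about 87-95% over ED50 50-500.

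The mean half-width is, to within simulation error, at least 1.645 times the empirical SD of λ̂. At ED50 50 µg and residual SD 10 it is 0.127 against 0.105 at true 1, and 0.138 against 0.117 at true 1.25. The misses therefore come from bias.

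**5. tmax with no dose trend.** From the design, the two slope estimates have variances proportional to 33.16 (rGlucagon) and 30.86 (LY3185643) and covariance 11.00, so the correlation is 11.00/√(33.16 × 30.86) = 0.344. With both true slopes zero, P(λ̂ < 0) = arccos(0.344)/π = 0.39. The ratio is then Cauchy with location 0.344 × √(33.16/30.86) = 0.357 and scale √(1 − 0.344²) × √(33.16/30.86) = 0.973. So P(0.5 < λ̂ < 2) = [arctan(1.688) − arctan(0.147)]/π = 0.28, and 72% fall outside. SD and sample size cancel. If tmax instead rises by 15 minutes from 10 to 200 µg (assumed within-subject SD 20-30 minutes), 12-30% fall outside 0.5-2.

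**The case against.** The strongest reply is that the documents do not show curvature in the studied range. Protocol 3.2.1 reports dose-dependent responses up to 0.2 mg, the top dose here, with maxima above it. Protocol 3.2 and 5.5 expect similar potency, and there the bias is 2-8% (ED50 50-500 µg) against a CI half-width of 0.09-0.23. If the response is linear, the SAP estimator is right. All of this stands, and it limits the weight of the curvature part.

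Some flexibility also exists. Dose-group tables will make the nine means visible. Protocol 10.3.3.2 allows PD parameters to be transformed. SAP 9.3.1 says "Population PK and exposure-response analyses may be performed using PK, PD and safety data", and SAP 3 says "If additional analyses are required to supplement the planned analyses described in this SAP, they may be performed". These soften the gap. None is a prespecified check, and none supplies an alternative λ.

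On tmax, flatness is an assumption: Protocol 3.2.1 gives peaks at 0.5 to 2 hours without saying whether they move with dose. A λ formed from near-zero slopes would usually carry a visibly wide interval. That is fair, but it does not give the number a meaning. Nor is λ the only input to the algorithms, since Protocol 3.1 also names time-action differences and further testing.

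A reader might infer that the straight-line CI is too narrow, or that coverage fails whenever potencies differ. Step 4 shows neither: the width is adequate, and coverage is near nominal at true 0.8.

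**Conclusion.** The point holds in a limited form. SAP 9.4.2 applies a raw-dose straight-line model to every PD parameter and, unlike the PK section, plans no check of it. That λ rests about 85% on the 200 µg doses follows from the design alone. The sizes of the bias rest on an assumed shared Emax curve and on assumed SDs:

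- small at the similar potency the protocol expects;
- larger if LY3185643 were the less potent drug (true 1.25), with serious undercoverage caused by bias;
- small, with near-nominal coverage, if it were the more potent (true 0.8).

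It would go too far to conclude that the glucose response is shown to flatten within 10-200 µg, or that λ will be wrong. The curvature part is worth considering. Taking tmax out of the λ analysis should be done: the common-intercept argument has no clear meaning for it, and a flat tmax makes its λ uninterpretable.

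**What to change.** In SAP 9.4.2:

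1. Drop tmax from the λ analysis and describe it by dose. This costs nothing.
2. Report a lack-of-fit comparison of model (1) with the nine dose means (9 − 3 = 6 df), as a diagnostic only. Protocol 10.3.3.2 already lists dose within treatment as a fixed effect. Under the step 4 settings its power is 80-100% at ED50 50 µg, 24-83% at 200 and 6-25% at 500, so a non-significant result would not demonstrate linearity.
3. Prespecify one shared-curve model with λ inside the dose term, for example Y = β0 + β1·(d·λ^(−Z))^γ + u + e, estimating log λ with γ bounded at 0.1-2. It contains model (1) at γ = 1. Always report its λ and 90% CI beside the straight-line estimate, and do not choose between them by a test.

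The cost is SAP text and a few lines of code, with no new data. The curved fit has limits:

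- It is less precise at equal potency: RMSE of log λ is 0.15 against 0.12 for the line (ED50 200, residual SD 20).
- Against a true Emax curve it is approximate: 0.96-1.00 at true 1 and 1.18-1.24 at true 1.25, with γ at its lower bound for ED50 of 50 µg or less.
- Unless curvature is strong, the 200 µg doses still dominate: 87% of the weight at γ = 1, 75% at 0.7 and 63% at 0.5.

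A straight-line fit that omits the 100 µg data should not be used as a correction. It is exact only at λ = 1. At true 0.8 it gives 0.84-0.93 over ED50 20-500, against 0.82-0.84 with the dose kept. If run at all, it should be labelled only as a check for equal potency.

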Parameters will be analyzed using a nonlinear mixed-effects model with period, treatment (LY3185643 or rGlucagon), and dose (within treatment) as fixed effects, baseline glucose as a covariate, and subject as a random effect. A conversion factor will be defined in the model for each parameter to estimate the relative potency of LY3185643 to rGlucagon. In addition, a conversion factor will be estimated between LY3185643 and rGlucagon

for multiple parameters simultaneously using a similar mixed nonlinear model approach to account for the correlation between parameters for the same subject.

All PD parameters including the baseline-corrected parameters will be summarized by dose group and tabulated. Summary statistics will be provided. The individual observed and mean (by dose group) time profile of the PD measurements after dosing will be plotted.

Immunogenicity: The frequency of antibody formation to LY3185643 will be determined. If a neutralization assay is performed, the frequency of neutralizing antibodies will be determined. The relationship between the presence (or absence) of antibodies and AEs will be assessed. Likewise, the relationship between the presence of antibodies and the PK parameters and PD response to LY3185643 will be assessed.

Interim Analysis: No interim analyses are planned for this study.

The Lilly study team is unblinded, and the investigator will remain blinded until the study is completed. Data may be analyzed while the trial is ongoing, but no changes to the study design are planned. An assessment committee will not be formed.

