### **10.3.3.2. Pharmacodynamic Statistical Inference**

PD parameters of interest may be transformed before statistical analysis if deemed necessary. Unless specified otherwise, parameters will be analyzed using a nonlinear mixed-effects model with period, treatment (LY3185643 or rGlucagon), and dose (within treatment) as fixed effects, baseline glucose as a covariate, and subject as a random effect. The use of other influencing variables as covariates will be explored as detailed in the statistical analysis plan.

A conversion factor will be defined in the model for each parameter to estimate the relative potency of LY3185643 to rGlucagon. In addition, a conversion factor will be estimated between LY3185643 and rGlucagon for multiple parameters simultaneously using a similar mixed nonlinear model approach to account for the correlation between parameters for the same subject. Model details will be discussed in the statistical analysis plan.

All PD parameters including the baseline-corrected parameters will be summarized by dose group and tabulated. Summary statistics will be provided. The individual observed and mean (by dose group) time profile of the PD measurements after dosing will be plotted.

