11. CHANGES FROM THE PROTOCOL SPECIFIED STATISTICAL ANALYSES

There were no changes from the protocol specified statistical analyses.

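### The SAP's PD model omits the protocol's period effect and baseline-glucose covariate and makes the joint conversion factor optional, while SAP section 11 declares no changes

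*SAP*

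**What the plan says.** Protocol 10.3.3.2 calls for a mixed model of nonlinear form and lists its terms: "period, treatment (LY3185643 or rGlucagon), and dose (within treatment) as fixed effects, baseline glucose as a covariate, and subject as a random effect". The synopsis gives the same model. Section 10.3.3.2 adds that "The use of other influencing variables as covariates will be explored as detailed in the statistical analysis plan", and that "a conversion factor will be estimated between LY3185643 and rGlucagon for multiple parameters simultaneously".

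SAP 9.4.2 sets out its model with the words "For each PD parameter, the linear model that is proposed to account for differences between LY3185643 and rGlucagon is", then gives

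Y_kl = β0 + β1·d_kl + β2·d_kl·Z_kl + u_k + e_kl,

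where Z is 1 for LY3185643 and 0 for rGlucagon. The conversion factor is λ = β1/(β1 + β2), reported with a 90% confidence interval from the nonlinear form of the same equation. On the joint analysis the SAP says only: "This model may be extended to allow for multiple parameter values, if deemed appropriate".

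On differences from the protocol, SAP 3 says "This SAP supersedes the statistical considerations identified in the protocol; where considerations are substantially different, they will be so identified". SAP 11 then says "There were no changes from the protocol specified statistical analyses".

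**The concern.** Two terms that the protocol names are missing from the SAP's equation, and an analysis that the protocol commits to has become discretionary. The section meant to record such differences reports none.

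This matters because λ and its interval are the planned relative-potency result. Protocol 3.1 says that relative potency will be used to direct changes to the artificial pancreas control algorithms. A reader of the study report who relies on SAP 11 would believe that λ came from the protocol's model. If period or baseline were added only after the data had been seen, the choice of model would be post hoc. Protocol 10.3.5 makes this more pressing, because it leaves the sponsor's team unblinded and able to analyse data during the trial.

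**Working it through.** **1. The two models side by side**

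| Element | Protocol (synopsis, 10.3.3.2) | SAP 9.4.2 | Reason given in SAP |
|---|---|---|---|
| Period | Fixed effect | Subscript only, no coefficient | None |
| Baseline glucose | Covariate | Not in the model | None |
| Treatment main effect | Fixed effect | Omitted | Yes: equal response expected at dose zero |
| Dose within treatment | Fixed effect | Linear slope for each treatment | Not at issue |
| Subject | Random effect | Random effect | Not at issue |
| Joint conversion factor | Committed | Optional | None |

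The algebra for λ is correct: β2 = β1(1 − λ)/λ follows from λ = β1/(β1 + β2). The subscripts index subject and period only, although three doses are given per period; that is a matter of notation.

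**2. Version gap.** The SAP was written against the protocol of 17 August 2016. The Amendment (a) log lists no change to Section 10 or to the statistical part of the synopsis, so a version mismatch does not explain the difference.

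**3. What subtraction already covers.** The SAP baseline-adjusts AUC and lists change from baseline in Cmax. The gap is therefore mainly in raw Cmax and tmax, and in the C-peptide parameters, where subtraction removes baseline C-peptide rather than baseline glucose. Subtraction of a predose value does not replace a period term.

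**4. Balance.** The example sequence table (Protocol Table APCA.5.1, SAP Table 1) is a 9×9 Latin square in which each dose occurs three times in each period. For completers, period is orthogonal to dose, so leaving it out does not bias λ. It moves period variation into the residual.

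**5. Size.** The documents give no SDs or slopes, so every input here is an assumption: 18 completers; slope 0.5 mg/dL per µg; λ = 1; baseline coefficient g = 0, 0.5 or 1 in absolute value; within-subject baseline SD sb = 2, 4 or 6 mg/dL; shift per period D = 0, 3 or 5 mg/dL; residual SD se = 8 or 12 mg/dL. Period means of 0, D and 2D have variance 2D²/3. Comparing the SAP model with the same model plus period and baseline:

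- Ratio of model standard errors of λ = √(1 + (g²·sb² + 2D²/3)/se²)
- Ratio of true sampling SDs of λ = √(1 + g²·sb²/se²)

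At the extreme corner (g = 1, sb = 6, D = 5, se = 8) the first is √(1 + (36 + 16.67)/64) = 1.350 and the second is √(1 + 36/64) = 1.250. Over all 3×3×3×2 = 54 combinations:

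- Model standard error: 0% to 35% larger, median 6%.
- True sampling SD: 0% to 25% larger, median 1.4%.

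**6. Simulation check** (random intercept with between-subject SD 10, 4000 runs per case)

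| g | sb | D | se | SE ratio (closed form) | True-SD ratio (closed form) |
|---|---|---|---|---|---|
| 1 | 4 | 3 | 12 | 1.073 (1.074) | 1.054 (1.054) |
| 0.5 | 6 | 5 | 8 | 1.195 (1.184) | 1.069 (1.068) |
| 1 | 6 | 5 | 8 | 1.359 (1.350) | 1.239 (1.250) |
| 0 | 6 | 5 | 8 | 1.136 (1.123) | 0.995 (1.000) |
| 1 | 6 | 0 | 8 | 1.248 (1.250) | 1.247 (1.250) |

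In the largest case the standard error is 0.0333 against 0.0245. With 162 − 18 − 2 = 142 within-subject degrees of freedom the t quantile is 1.656, so the 90% half-widths are 1.656 × 0.0333 = 0.055 and 1.656 × 0.0245 = 0.041. With no period or baseline effect the standard errors are 0.0367 and 0.0368, so the extra terms cost nothing visible.

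Over 12 completer cases mean λ was 1.000 to 1.001 and coverage of the SAP model's 90% interval was 89.5% to 94.5% (Monte Carlo error about 0.5 points). With 19 random partial sequences added (4 cases, 1500 runs each), coverage was 89.9% to 92.3% and mean λ 0.999 to 1.001.

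**The case against.** The strongest reply is that the model was delegated. Protocol 10.3.3.2 applies its model only where nothing else is specified and leaves model details to the SAP. SAP 3 says that the SAP prevails and promises to flag only substantial differences. The core is kept: a random subject effect, treatment-specific slopes, the nonlinear form and λ. The omission of the treatment main effect is explained. This stands as far as permission goes, although the synopsis carries no such proviso. It does not make a declaration of no changes true. The protocol named period and baseline glucose itself and left only further covariates to the SAP, which names none. The joint factor was a committed analysis, not a model detail.

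The second reply is that little is at stake, and much of this stands. λ is not biased, and coverage does not fall materially below 90%. The 35% is one corner of an assumed grid and concerns the model standard error. The true sampling SD rises by 5% or less at 39 of the 54 points, and with balance omitting period costs no true precision. The upper end describes raw Cmax, not a baseline-adjusted response. Protocol 5.4 expects glucose back at baseline within 4 hours, which points to a small baseline SD. No numerical consequence has been shown for the joint factor.

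**Conclusion.** The concern holds and should be fixed. The documentary part needs no assumptions: two named terms are absent without a reason, a committed analysis has become optional, and SAP 11 denies any change despite the promise in SAP 3.

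The statistical consequence is modest and concerns precision. Under the assumed inputs the interval for λ ranges from no wider to about a third wider than it need be, with a median excess of 6%. If response does not vary with period or predose glucose, nothing is lost. The statements that λ is unbiased and the interval at worst too wide rest on two conditions. The actual schedule must be balanced like the table, which is marked as an example, and dropout must be unrelated to dose or response, since only random dropout was simulated.

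**What to change.** Take one of two routes for the model in SAP 9.4.2:

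- Add period as a fixed effect and the dose-specific mean predose glucose as a covariate, in both the linear and nonlinear forms, and index the model by subject, period and dose within period.
- Keep the present model and list each dropped term in SAP 11 with its reason.

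Under either route, state whether the joint multi-parameter conversion factor will be estimated, and correct SAP 11 so that it lists, with reasons, every protocol term or analysis dropped or made optional.

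The cost is SAP wording and code. All variables are already collected. The two terms use 3 degrees of freedom (2 for period, 1 for baseline) out of 18 × 9 = 162 completer observations. Disclosure alone is one entry in SAP 11.
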